9.3 Protocol Deviations

All protocol deviations will be included as a categorized listing. Safety and mITT analyses will include all enrolled subjects with all available data. Subjects with major deviations will be excluded from the per protocol analyses. Major deviations will be defined as anyone who was enrolled and has completed at least one experimental session but found to not meet inclusion/exclusion criteria during the course of the study. The number of subjects in each protocol deviation category listed below will be summarized by MDMA group, and individual subjects will be listed in the appendix.

Possible protocol deviations include the following seven categories:

- Subject entered study but did not meet criteria
- Subject developed withdrawal criteria but was not withdrawn
- Subject received excluded concomitant treatment
- Protocol procedure not performed per protocol
- Subject received incorrect treatment or incorrect dose
- Protocol procedure performed out of range
- Miscellaneous

Per Amendment 6, three subjects were found to have undisclosed exclusionary conditions during the course of their treatment in the study. As these conditions did not pose a safety risk, the subjects completed study procedures, but an additional three subjects were added to the total study enrollment. An additional two subjects withdrew or were withdrawn by the investigator prior to their second experimental session and were replaced per protocol. These subjects will be included in the Safety and mITT population.

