9.1 Analysis Populations

Modified Intent-to-treat (mITT): all subjects who were randomized, received at least one experimental session and completed at least one outcome assessment

Per protocol (PP): all subjects who completed two experimental sessions and primary outcome assessment in Stage 1 and did not experience a major protocol deviation

Crossover: all subjects who completed Stage 2 in addition to completing Stage 1

Safety: all subjects who receive any study treatment

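### The SAP's definition of a major deviation turns only on eligibility, so a subject given a dose other than the one randomised would stay in the per-protocol set under the assigned arm

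*SAP*

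**What the plan says.** SAP 9.1 defines the PP population as "all subjects who completed two experimental sessions and primary outcome assessment in Stage 1 and did not experience a major protocol deviation". It sets no condition on the dose actually received.

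SAP 9.3 then says what makes a deviation major: "Major deviations will be defined as anyone who was enrolled and has completed at least one experimental session but found to not meet". The rest of that sentence names the eligibility criteria, and they are the only trigger. The definition has no list of examples and no provision for case-by-case judgement. The consequence is also stated there: "Subjects with major deviations will be excluded from the per protocol analyses".

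The same section lists seven deviation categories. Three matter here, and each has its own line:

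- "Subject entered study but did not meet criteria"
- "Subject received excluded concomitant treatment"
- "Subject received incorrect treatment or incorrect dose"

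All seven are to be summarised by MDMA group, with subjects listed in an appendix. Apart from the eligibility rule, 9.3 links no category to PP exclusion.

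**The concern.** This is a dose-response study. Protocol 5.2.3 keeps procedures the same across sessions apart from the dose, so the dose received at the two blinded sessions is what separates the arms. A PP set is meant to hold subjects treated as the protocol intended. Here it screens for eligibility but not for dose, the departure that bears most directly on the comparison. The SAP foresees dosing errors, since it gives them a category, but it does not act on them.

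The arms are small: 12, 9 and 5 under SAP 6.0. One subject counted under the wrong dose can visibly move an arm mean, most of all in the comparator arm. If the rule is left until such a case appears, the decision to keep or drop the subject may be taken with the outcome in view.

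**Working it through.** **1. Reading the definitions together.**

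| Deviation category (SAP 9.3) | Meets the major definition? | Removed from PP? |
|---|---|---|
| Entered without meeting criteria | Yes, after at least one session | Yes |
| Developed withdrawal criteria, not withdrawn | Possibly, where the withdrawal criterion is also an exclusion criterion (Protocol 5.4) | Unclear |
| Excluded concomitant treatment | Not by its own label; possibly through the eligibility criteria (step 2) | Unclear |
| Incorrect treatment or dose | No | No |
| Procedure not performed, procedure out of range, miscellaneous | Not as such | No |

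No other section adds a dose condition to PP or moves a misdosed subject to the arm of the dose received. For incorrect dose the result follows directly from the wording.

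**2. Excluded concomitant treatment.** SAP 9.3 lists it apart from eligibility, which suggests it is not major. Against that, inclusion criteria 7 to 9 restrict new therapy, psychiatric medication during the study and most medication in the week before a session. Exclusion 12 bars ongoing psychiatric drugs. Protocol 5.4 names excluded medications among the exclusion criteria a subject may develop, and Protocol 5.2.3 has eligibility reviewed at each experimental session. Either reading can be defended.

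**3. Shift in an arm mean (illustration).** The documents give no number of misdosed subjects and no size of effect for one. Assume one subject whose CAPS change differs by Δ from what the assigned dose would have produced. The arm mean moves by Δ/n.

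| Assumed Δ | n=12 | n=9 | n=5 |
|---|---|---|---|
| 10 | 10/12 = 0.8 | 10/9 = 1.1 | 10/5 = 2.0 |
| 20 | 20/12 = 1.7 | 20/9 = 2.2 | 20/5 = 4.0 |
| 30 | 30/12 = 2.5 | 30/9 = 3.3 | 30/5 = 6.0 |

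These use the randomised numbers. PP arms may be smaller, and the shift would then be larger.

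**4. Effect on power (illustration).** The plan's own figure comes first. Protocol 12.1 gives power 0.33 for 18 versus 5 at effect size 0.8. A two-sided t-test at 0.05 with 21 degrees of freedom has noncentrality 0.8 × √(18×5/23) = 1.58 and power 0.327, so the figure is reproduced.

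Now suppose one of the five comparator subjects received an active dose, responded to it accordingly, and stayed in PP as randomised, with the SD unchanged. The effect becomes 0.8 × (1 − 1/5) = 0.64.

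| Case | Undisturbed | Subject kept | Subject excluded |
|---|---|---|---|
| One comparator subject given an active dose, 18 vs 5 | 0.327 | 0.227 | 0.281 (18 vs 4) |
| Same, SAP numbers with actives pooled, 21 vs 5 | 0.339 | 0.235 | 0.290 (21 vs 4) |
| One active subject given the comparator dose, 18 vs 5 | 0.327 | 0.297 | 0.322 (17 vs 5) |

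The loss is concentrated in the comparator arm. These figures are for the pooled t-test, which is exploratory in SAP 9.9.3. They are not for the three-group ANOVA in 9.9.1.

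**The case against.** The strongest reply has four parts.

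*Nothing has gone wrong.* SAP 9.3 describes three subjects with undisclosed exclusionary conditions and two early withdrawals, and reports no misdosing. Dosing uses one numbered container per subject per session, with web-based assignment. This stands as a statement about frequency. It does not repair the rule, which SAP 2.0 presents as a priori and to be final before any unblinded, inferential or descriptive analysis.

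*A wrong dose would be visible.* Deviations are listed by subject, and SAP 9.6 tabulates total MDMA for the PP population. This also stands, but display does not change who is analysed.

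*PP carries no assigned efficacy analysis.* SAP 9.9.1 and 9.9.2 name no population. Outside its definition, PP appears only in the disposition and dosing summaries and in a general reference in 9.3 to per-protocol analyses. A reader might infer that the primary result is exposed to this defect; the documents do not support that. What is exposed is an implied analysis, in a pilot that describes itself as underpowered.

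*Excluded medication is already covered.* A reader might infer that a subject taking excluded psychiatric medication before visit 12 certainly stays in PP. The eligibility wording in working step 2 prevents that conclusion, and a subject who stops before the second session leaves PP anyway. The text is ambiguous on this half.

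A further caution is that PP is not an as-treated analysis. The cumulative dose varies within each arm by design, because the supplemental dose is optional: 40–60, 100–150 and 125–187.5 mg. That variation is not a deviation, and any new wording has to say so.

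**Conclusion.** The point holds for incorrect treatment or dose at blinded sessions 1 and 2: as written, such a subject remains in PP under the assigned arm. This is a stated rule that yields the wrong set, not merely missing detail. For excluded concomitant treatment the finding is only that the SAP supports two readings and should choose one.

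The actual effect is unknown and may be nil. The 1.7, 2.2 and 4.0 point shifts rest on an assumed 20-point difference in a single subject and on randomised arm sizes. The power figures also assume response by dose received and a constant SD. They show how sensitive small arms are and are not evidence that any result has been distorted. The change is worth making because it is cheap and has to precede the analysis to be credible.

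**What to change.** Before any unblinded analysis, add to SAP 9.3:

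> Major deviations also include receipt at session 1 or 2 of a treatment or dose other than the one randomised (not giving the optional supplemental dose is not a deviation), and receipt before visit 12 of psychiatric treatment the protocol excludes (rescue medication the protocol permits is not a deviation).

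Have the classification made by staff blind to visit 12 CAPS. Whoever judges a dosing error must see the allocation and the dose given, so it is the outcome that should be withheld.

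State in SAP 9.9.1 which population each efficacy analysis uses, so that the role of PP is explicit.

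The cost is a few lines of SAP text. PP may lose a subject, who stays in the mITT and Safety populations. Dosing, study conduct and data collection do not change.

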9.4 Pooling of Investigator Centers

All subjects in this study come from one investigational center.

9.5 Baseline Values

Baseline values are from screening/baseline visit for all measures, except C-SSRS. For C-SSRS, pre-enrollment scores will be used as a measure of ‘lifetime’ suicidal ideation and behavior, and preparatory session 2 (visit 2) prior to drug administration will be used as ‘baseline.’ If a subject was not administered the C-SSRS at preparatory session 2 (visit 3), then ‘baseline’ scores will be visit 4 pre-drug C-SSRS observation.

9.6 Subject Disposition and Dosing Summary

All subjects enrolled in the study (i.e., who sign informed consent and complete inclusion/exclusion criteria) will be included in the summary of subject disposition and accountability. No inferential statistical tests will be performed. The tabulation of number of subjects in each treatment group and overall will be displayed for all subjects in the Safety Population, in the mITT Population, and in the PP Population. The number and percent of subjects who completed or discontinued the study will be displayed for each treatment group and overall together with reasons for early termination, where the percent is with respect to the total number of randomized subjects in that treatment group. The timepoint of doses and total MDMA (mg) administered will be summarized by treatment group for the Safety, mITT and PP Populations.

9.7 Demographics and Baseline Characteristics

Subject demographic data and baseline characteristics will be summarized descriptively by treatment group and overall. The demographic data and baseline characteristics will be summarized for the mITT and Crossover Populations.

9.8 Prior and Concomitant Medications

The number and percent of subjects who took medications prior to and after signing informed consent will be summarized descriptively for each treatment group. Concomitant medications will be summarized similarly. Prior and concomitant medications will be summarized for the Safety Population. Psychiatric medications will be coded to common drug classes and terms.

9.9 Efficacy Analyses

For all primary, secondary and exploratory endpoints descriptive statistics (n, mean, standard deviation, median, range, effect size (for measures of interest), or counts and percentages where appropriate) will be provided by treatment group.

Effect size (Cohen's *d*) for each treatment group will be determined by employing an independent-groups pretest-posttest design (IGPP), where the mean difference in the pretest-posttest is divided by the standard deviation of raw scores, and then the control group effect size is subtracted from the experimental group effect size [1].

$$d_{IGPP} = \frac{X_{\text{postT}} - X_{\text{PreT}}}{S_T} - \frac{X_{\text{postC}} - X_{\text{PreC}}}{S_C}$$

X = treatment means

S_T and S_C = pooled SD of pre- and post-test by group

9.9.1 Primary Efficacy Analyses

Clinician Administered PTSD Scale-4 (CAPS-4)

The primary efficacy evaluation is the change from baseline to the primary outcome timepoint (visit 12) in the CAPS-4 Global Severity score of PTSD (difference score). The primary efficacy comparison will be made with ANOVA at an alpha level of 0.05. If the primary hypothesis rejects, pairwise comparisons among the treatment groups will be made with t-tests. If the parametric assumptions for the ANOVA and t-test analyses are not met, the analogous nonparametric methods will be used (Kruskall-Wallis, Wilcoxon Rank-Sum).

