12.0 Data Analysis

The Sponsor will judge the clinical and statistical significance of the study based on a comparison of observer-blind data collected at baseline and the primary endpoint using the primary outcome measure, which is the CAPS. Descriptive statistics will be computed overall and within the three dose conditions for all available data from outcome measures, including minimum, maximum, average, and standard deviation. Distributional characteristics will be examined for outliers and extreme values and, if either is evident, nonparametric statistics will be utilized in the analysis. Effect size of the three doses for all outcome measures for Stage 1, Stage 2, and 12 months after the final experimental session will be estimated using Cohen's techniques.

The Sponsor will examine each active dose group and the comparator dose group for homogeneity through comparing demographic characteristics. There is no expectation that conditions will differ in composition by gender, race or ethnicity, duration of PTSD diagnosis or presence versus absence of other permitted psychiatric disorders, as depression. However, owing to small sample size, such variations may arise by chance.

The Sponsor will examine CAPS scores for the primary outcome analysis at baseline and the primary endpoint in each active dose and comparator dose conditions. Active dose 1 and active dose 2 CAPS data at the primary endpoint will be tested for equivalence using confidence intervals. If the two groups are found to be equivalent, then outcomes for the active dose groups will be combined and will be tested for significant differences from the comparator group using difference scores in independent sample t-tests, with p value set at 0.05. If CAPS scores for active dose 1 are not equivalent to active dose 2, then analysis of variance (ANOVA) will be used to compare outcomes from all three groups. Additional exploratory analyses comparing the effect of a third experimental session with either active dose 1 or active dose 2 may be conducted if sufficient group sizes are attained, and analyses comparing outcomes at third session may be conducted with and without active dose 2 participants who elected to take active dose 1 during the third experimental session.

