9.9.2 Secondary Efficacy Analyses

The secondary efficacy analyses will be made with ANOVA comparing change from baseline (Baseline) to the primary outcome timepoint (visit 12) of all the secondary measures, following the same methodology used for the primary endpoint. If the parametric assumptions for the ANOVA analyses are not met, the analogous nonparametric methods will be used (Kruskall-Wallis, Wilcoxon Rank-Sum).

PTSD Diagnostic Scale (PDS) total score will be analyzed in the same manner as the CAPS-4 global scale primary analysis.

Global Assessment of Functioning (GAF) total score will be analyzed in the same manner as the CAPS-4 global scale primary analysis.

Beck Depression Inventory-II (BDI-II) total score will be analyzed in the same manner as the CAPS-4 global scale primary analysis.

Post Traumatic Growth Inventory (PTGI) total will be analyzed in the same manner as the CAPS-4 global scale primary analysis.

Dissociative Experiences Scale-II (DES-II) total will be analyzed in the same manner as the CAPS-4 global scale primary analysis.

Pittsburgh Sleep Quality Index (PSQI) global scores will be analyzed in the same manner as the CAPS-4 global scale primary analysis.

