9.9.3 Exploratory Analyses

Clinician Administered PTSD Scale-4 (CAPS-4)

- The percentage of subjects who achieve a 30% drop in CAPS-4 global score at the primary endpoint (visit 12) will be an indirect measure of clinical significance. Descriptive statistics will be computed and displayed by Stage 1 treatment groups.
- The percentage of subjects who no longer meet PTSD diagnostic criteria according to the CAPS-4 at the primary endpoint (visit 12) will be an indirect measure of clinical significance. Descriptive statistics will be computed and displayed by Stage 1 treatment groups.

- CAPS-4 Subscale Scores (B, C, D, F) at the primary endpoint (visit 12) will be analyzed in the same manner as the primary analysis of the global score. Descriptive statistics will be computed and displayed by Stage 1 treatment groups.
- Active dose 1 (125mg) and Active dose 2 (100mg) CAPS data at the primary endpoint will be tested for equivalence using confidence intervals. If the two groups are found to be equivalent, then outcomes for the active dose groups will be combined and will be tested for significant differences from the comparator group using difference scores in independent sample t-tests, with p value set at 0.05.
- Comparison of the effect of a third experimental session with either Active dose 1 or Active dose 2 may be conducted if sufficient group sizes are attained, and analyses comparing outcomes at third session may be conducted with and without Active dose 2 participants who elected to take Active dose 1 during the third experimental session.
- Two regression analyses will be conducted using (1) all subjects with a Frequency score of 2 or greater and an Intensity score of 2 or greater on the CAPS Associated Features 29 or 30 at baseline and (2) baseline DES-II total score as baseline covariates to determine whether the dissociative subtype of PTSD is predictive of treatment outcomes.

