- Here is my suggestion for wording the bullet point above: To determine if baseline variables that assess disassociation are predictive of CAPS Global Severity Score at the Primary Endpoint (dependent variable), a multiple regression analysis will include the following independent variables at baseline (1) dichotomous variable defined as Frequency of 2 or greater and Intensity of 2 or greater on the CAPS Associated Features 29 or the alternative (2) dichotomous variable defined as Frequency of 2 or greater and Intensity of 2 or greater on the CAPS Associated Features 30 or the alternative, and (3) DES-II total score.
-

PTSD Diagnostic Scale (PDS)

A repeated measures analysis of variance (ANOVA) will be performed upon PDS scores at baseline, after experimental sessions (visits 4 and 13) and at the end of Stage 1 (visit 17), with p value set at 0.05. Stage I treatment group will serve as a between-subjects factor. Results of repeated measures ANOVA analysis will be used to examine the effects of each experimental session on self-reported PTSD symptom severity.

Clinician Administered PTSD Scale-4 (CAPS-4) and PTSD Diagnostic Scale (PDS)

PDS and CAPS scores will be correlated via Pearson's product moment correlation at baseline and the timepoint that the primary efficacy is measured to provide a comparison of a self-report measure with a clinician-administered measure of PTSD symptoms.

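### No planned efficacy comparison adjusts for baseline CAPS, so with five comparator subjects the change-score contrasts are exposed to chance baseline imbalance

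*SAP*

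**What the plan says.** SAP 9.9.1 defines the outcome: "The primary efficacy evaluation is the change from baseline to the primary outcome timepoint (visit 12) in the CAPS-4 Global Severity score of PTSD". The three groups are compared by ANOVA at 0.05, then by pairwise t-tests if the ANOVA rejects, with rank tests as a fallback. SAP 9.9.2 carries this over to the other scales: "The secondary efficacy analyses will be made with ANOVA comparing change from baseline (Baseline) to the primary outcome timepoint (visit 12").

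The pooled comparison takes the same form. If the two active doses are judged equivalent, SAP 9.9.3 (exploratory) has the combined group "tested for significant differences from the comparator group using difference scores in independent sample t-tests, with p value set at 0.05". In Protocol 12.0 the same comparison is the primary one: the combined outcomes "will be tested for significant differences from the comparator group using difference scores in independent sample t-tests". If the doses are not equivalent, "then analysis of variance (ANOVA) will be used to compare outcomes from all three groups"; this branch names neither difference scores nor a covariate.

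Baseline covariates appear only in the exploratory regressions of SAP 9.9.3, with this aim: "To determine if baseline variables that assess disassociation are predictive of CAPS Global Severity Score at the Primary Endpoint (dependent variable"). Their predictors are CAPS associated-features items and the DES-II. Neither treatment group nor baseline CAPS severity is named. The PDS repeated-measures ANOVA uses baseline PDS as a time point, not as a covariate.

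The baseline is available, since SAP 9.5 says "Baseline values are from screening/baseline visit for all measures, except C-SSRS". Protocol 12.0 expects the groups to be alike in demographics, PTSD duration and comorbidity, then adds: "However, owing to small sample size, such variations may arise by chance". It does not mention CAPS there, and no analysis takes such differences into account.

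**The concern.** A change-score comparison is a baseline-adjusted comparison with the baseline slope fixed at 1. If the true slope is lower, the group that happens to start higher shows a larger fall for reasons unrelated to dose. Over repeated randomisations this averages out, so neither bias nor type I error is the issue. In the one trial that is run, the contrast carries (slope − 1) times whatever baseline difference arose, and with five comparators that difference is often large.

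This matters because the pilot's stated product is an effect-size estimate for pooling across studies and for sizing later ones (Protocol 12.1, SAP 7.0). Precision and robustness of the estimate are therefore what the trial has to deliver.

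**Working it through.** **Inputs.** Allocation 12:9:5 (SAP 6.0; Protocol 5.3 has 9:9:5); two-sided alpha 0.05 (SAP 9.0); d = 0.8 and power 0.33 for 18 v 5 (Protocol 12.1). The baseline-endpoint correlation r and the ratio k = SD at visit 12 / SD at baseline are not given. I assume r = 0.3, 0.5, 0.7 and k = 1, 1.25, 1.5. Entry at CAPS 50 or above (Protocol 4.2.1) narrows the baseline spread, so k above 1 is plausible.

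**The plan's own figure.** Noncentral t, 18 v 5, gives 0.327 at d = 0.8 (stated 0.33) and 0.546 at d = 1.1 (stated 0.55). For 21 v 5 at d = 0.8 it gives 0.339.

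**Chance imbalance.** SD of the 12 v 5 baseline difference = √(1/12 + 1/5) = 0.532 baseline SD. A difference above 0.5 SD arises in about 35% of randomisations.

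**Shift carried by the change score.** The slope is rk, so the shift is (1 − rk) × 0.532:
- k = 1: 0.37 / 0.27 / 0.16 baseline SD for r = 0.3 / 0.5 / 0.7.
- k = 1.5: 0.29 / 0.13 / 0.03, the last with sign reversed because rk = 1.05.

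**Variance ratio, ANCOVA to change score** (common slope, equal residual variance): k²(1 − r²)/(1 + k² − 2rk) × 22/21. The last factor is the cost of estimating the slope on 23 within-group degrees of freedom. Example, k = 1 and r = 0.5: 0.75/1 × 22/21 = 0.786.

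| k | r = 0.3 | r = 0.5 | r = 0.7 |
|---|---|---|---|
| 1 | 0.681 | 0.786 | 0.890 |
| 1.25 | 0.822 | 0.935 | 1.027 |
| 1.5 | 0.913 | 1.010 | 1.045 |

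Simulation (40,000 trials per cell) agrees to within 0.01. In all nine cells the ANCOVA error had absolute correlation of at most 0.012 with the imbalance; the change score reached 0.60. Truncating the baseline distribution, to mimic the entry rule, left every ratio within 0.012 of the formula.

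**Break-even.** ANCOVA gains when 1 − slope exceeds residual SD/√21. With residual SD of 0.95 or 1.2 baseline SD this is 0.207 or 0.262, so it gains below a slope of about 0.79 or 0.74.

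**Unequal slopes** (200,000 trials each; residual SD in brackets):

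| Active slope | Comparator slope | Variance ratio | Correlation with imbalance, change / ANCOVA |
|---|---|---|---|
| 0.7 (0.71) | 0.3 (0.95) | 0.77 | −0.54 / −0.23 |
| 0.3 (1.0) | 0.7 (0.7) | 0.90 | −0.46 / +0.24 |
| 0.3 (0.95) | 0.9 (0.4) | 1.13 | −0.38 / +0.41 |
| 0.5 (1.2) | 1.0 (0.5) | 1.16 | −0.18 / +0.30 |
| 0 (1.0) | 1.0 (0.4) | 1.36 | −0.35 / +0.55 |

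A wider grid (active slope 0.3 or 0.5, active residual SD 0.95, comparator residual SD 0.95 or 0.5) gave ratios of 0.52 to 0.93 for comparator slopes of 0.3 to 0.7, and 1.04 to 1.23 for slopes of 0.9 to 1.0.

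**Power after adjustment**, 21 v 5, d = 0.8, common slope, r = 0.3 / 0.5 / 0.7: 0.464 / 0.413 / 0.373 at k = 1; 0.398 / 0.358 / 0.331 at k = 1.25; 0.365 / 0.335 / 0.326 at k = 1.5. The unadjusted figure is 0.339. Simulated type I error is nominal for both methods (0.048 change score, 0.049 ANCOVA).

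**The case against.** The planned test is valid, it answers an objective framed as change, and the documents cannot show which method is more precise here. Where k exceeds 1, which the entry rule makes plausible, the gain shrinks or turns into a small loss. A comparator slope nearer 1 than the active slope is also credible: Protocol 5.1.1 calls CAPS retest reliability good, and Protocol 2.4 expects less therapeutic effect at 40 mg. The active arms supply 19 of the 23 within-group degrees of freedom (83%), so their slope would largely be imposed on the five comparators. All of this stands. It limits the size of the benefit, and the slope pattern remains conjecture.

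A second argument concerns unequal variances. With slopes of 0.5 and residual SD of 1.4 in the comparator against 0.95 in the active arms (assumed), the 95% interval for 125 mg v 40 mg from ANCOVA covers about 0.89. The planned three-arm ANOVA variance gives about 0.90 and a pairwise pooled t-test 0.91, so ANCOVA adds little to this weakness. An unequal-variance t-test covers 0.945, but the plan does not specify one.

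Third, the effect size in SAP 9.9 and the rank-test fallback would stay unadjusted. That is a difference in reporting; it does not make an adjusted primary analysis unsound.

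Finally, group summaries would reveal an imbalance and SAP 9.0 allows labelled post-hoc analyses. But adjustment chosen after seeing the imbalance carries less weight than adjustment specified beforehand.

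**Conclusion.** The point holds. No listed efficacy analysis adjusts a treatment contrast for baseline CAPS, and the comparator arm has five subjects. This is a matter of precision and of dependence on chance imbalance; the plan's validity is not in question.

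Under a common slope and equal residual variance, ANCOVA changes the contrast variance by between −32% and +5% over the assumed range and removes the dependence on imbalance on average. With unequal slopes it gains 7% to 48% for comparator slopes of 0.3 to 0.7 and costs 4% to 23% for 0.9 to 1.0; the extreme case tried costs 36%. At a comparator slope of 0.9 its dependence on imbalance is about that of the change score, and at 1.0 it is larger.

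The change is worth making, with medium confidence, because r, k and the slopes are assumptions. Power for 21 v 5 stays between 0.33 and 0.46, so the trial remains underpowered either way.

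**What to change.** Before any unblinded analysis, as SAP 2.0 already requires for finalising the plan:

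- In SAP 9.9.1, make the primary analysis an ANCOVA of visit 12 CAPS on treatment group with baseline CAPS as covariate. Using change as the outcome gives the same contrast.
- Prespecify a common slope. Do not add a data-driven test of slopes, which five comparators cannot support.
- Report the pairwise contrasts with 95% confidence intervals from this model. The rule that pairwise tests follow a significant overall test need not change.
- Keep the unadjusted change-score ANOVA as a sensitivity analysis. It shows how much the adjustment matters and preserves the change-score scale for the pooling planned in Protocol 12.1.
- In SAP 9.9.2, do the same for PDS, BDI-II, GAF, PSQI and DES-II, each on its own baseline. Exclude PTGI, whose reference period changes after baseline (Protocol 5.1.1).
- Leave the rank-test fallback as it is, and label the SAP 9.9 effect size as unadjusted.
- Make the matching edit in Protocol 12.0.

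The cost is a short rewording, one degree of freedom and no new data. The variance penalty in unfavourable cases is about 5% under a common slope and equal residual variance. It is larger, 4% to 23% in the grid above, if the comparator slope is near 1 while the active slope is lower.
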